4.2 Data Analysis

In WP1, data from the roundtables shall not be formally analysed but insights gained will be developed into a report and used throughout the project, and specifically to inform the background context for the prioritisation and standards development of the digital referral tool. Where a consensus on priorities cannot be reached within or across workshops, the research team, in close collaboration with the advisory groups, will make the final decisions using a Consensus Voting approach.

In WP2, we shall design a standards-compliant technical architecture for the system, emphasising the need for interoperability with NHS systems. This will include consideration of how the tool complies with NHS referral standards (e.g. BaRS standard [34]) and with the NHS app [35]. We shall also undertake an assessment of each CAMHS service's capacity and capability to implement the referral tool using the empirical NASSS framework [36]. We will employ a light touch version of the framework to assess CAMHS site's suitability to participate in the programme. We will then run a workshop with each of the chosen sites to undertake a full assessment of their capability to implement, identify risks to implementation, create a plan to manage and mitigate them.

Our user-centred co-design approach will follow the UK's Government Digital Standards approach across the four stages of User Research: Discovery, Alpha, Beta, Live [37]. Each of the first two phases, described above, will involve a 1-hour co-design workshop with key stakeholders (n=25 key referrers, including GP, school and health professionals, CYP, families and carers). Our aim to include a diversity of referrers (including diversity of: referrer type; demographics; urban/rural; CAMHS configuration – where applicable; personal characteristics of CYP referred – key diversity elements are drawn from our work in EN-CAMHS 1.)

WP3 Quantitative data analysis: We shall evaluate how referrers engage with the referral tool analysing engagement / usage analytics from the digital tool following the AMUsED framework [42]. Specifically, we will summarise usage over time to evaluate whether it is an acceptable referral

method and we will explore whether this differs between type of referrer. We shall explore 'effective engagement' with the tool: the ability of referrers to complete a successful referral with the tool. A successful referral can mean either a referral to CAMHS or to an alternative source of support for the CYP. We shall analyse the rate of successful referrals made using the tools against those made using traditional referral processes.

Qualitative data analysis: We will conduct qualitative interviews (n=25) with referrers who have used the digital tool to highlight any potential barriers to implementation. Additionally, WP3 Qualitative data analysis: Anonymised transcripts will be analysed using NATCEN Framework Analysis methodology set out by Ritchie and Spencer [43], outlined in Ritchie et al. [44], and using Nvivo 12, as this has a Framework Matrices Tool [45], allowing for both inductive and deductive coding. Coders will meet regularly to discuss codes and develop a provisional framework. During constant comparison of new data, this provisional framework will be amended to accommodate new codes and remove old codes that become superfluous. The final coding framework will be presented to the study advisory group to ensure interpretations of data remain grounded in the experience of mental health services. Analysis will occur in parallel to data collection. The whole team will agree when data saturation has occurred.

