4.1 Data Collection

Work Package 1 (WP1), Months 3-12 (Leads: MQ, PW, PB) - Requirements Prioritisation

Aims:

- We shall hold 2 x roundtable events (Manchester and London) to gather feedback and input from senior stakeholders (e.g. NHS England senior leaders; commissioners, CAMHS leaders).
- With our partner MQ, we shall conduct 6 stakeholder focus groups with CYP, families/carers and professionals including GPs, to collaboratively prioritise requirements (identified in EN-CAMHS 1) for the revised digital tool. We aim to recruit up to 10 stakeholders per group, therefore 60 participants in total. We shall use the MoSCoW prioritisation method [29] collaboratively as we have done in a number of other NIHR funded digital health projects. As part of this prioritisation process, each of the existing 11 interactive CAMHS referral forms created by individual CAMHS in England will be rated using the System Usability Scale [30] and using criteria from the EN-CAMHS 1 focus groups (e.g. navigability, clarity of language, accessibility).

The technical project team will use the information from the roundtable and stakeholder meetings about the broader technical mental health landscape alongside their expert digital health software knowledge to develop a set of technical standards relevant for the CAMHS referral process. The costed software engineer will align with and extend existing NHS referral standards and interoperability standards to achieve this aim.

Work Package 2 (WP2) (PW, RE, JEC, Digital Health Software Team, VB): Months 3-12 - Co-Design and Tool Implementation

Aims:

- Onboard 5-8 CAMHS providers (with different characteristics and served populations) who are willing and can support an evaluation of the digitally-enhanced CAMHS tool in collaboration with our partners, NHS England.
- Workshops with 5-8 Trust staff from each provider.
- Co-design the tool with CAMHS stakeholders (2 x 1-hour workshops with 25 referrers).

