We shall use the NASSS-CAT toolkit [32] to guide the implementation and evaluation of the digital tool across CAMHS sites. This entails running a NASSS-CAT workshop with key stakeholders from each CAMHS service in order to introduce and complete the assessment as well as create a risk management and mitigation plan. The workshop will identify gaps in information that will need to be identified and incorporated. Once this is done, the risk plan will be regularly reviewed throughout the implementation process. Insights from this will be turned into an implementation toolkit that sets out a standardised evidence-based approach along with common risks and how they can be managed or mitigated. We shall also use the NASSS-CAT implementation toolkit to explore the potential, enablers and barriers of embedding a new CAMHS referral mechanism across different types of referrers and across CAMHS with various configurations. The NASSS-CAT toolkit will be used to guide implementation discussions with key stakeholders. Specifically, we will use the NASSS framework to address key considerations for the implementation digital transformation covering the key NASSS areas: the illness/condition in question; the technology; the value proposition; the intended adopters; the organisation; external context for innovation. The questions from the NASSS-CAT toolkit on these areas will be tailored for the EN-CAMHS project and used to structure the topic guides for interviewers with referrers.

We shall collect referral data from each referrer and from the CAMHS site referred into. We shall collect number of referrals made via the digital tools and numbers made by traditional referral mechanisms. We shall collect usage and engagement data with the tool, including numbers of referrals completed to an endpoint (either referral sent to CAMHS or to alternative help). We shall collect data on accepted/rejected referrals made by participant referrers to CAMHS using a) the tool and b) traditional modes of referral. Co-design workshops with each CAMHS provider will help us understand which data can be captured, and how each provider records the data.

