6 SAMPLE AND RECRUITMENT

6.1 Eligibility Criteria

6.1.1 Inclusion criteria

Throughout the project, participants will be included if they are:

- Aged 16+.
- CAMHS Stakeholders who have experience with the CAMHS referral process since 2019, these may include:
 - CAMHS Staff: we will include any staff who currently work in CAMHS services.
 - Collaborators: We will include collaborators who have direct experience of the current referral process for CAMHS.
 - CYP: We will be recruiting CYP who have been referred to CAMHS regardless of whether they were accepted into the service or not.

- Key referrers: We would ask that these individuals have had experience referring CYP to CAMHS, regardless of how many times.
- Parents/carers: we will ask parents/carers who have experience of their child or a child in their care having been referred to CAMHS, regardless of the outcome of the referral.
- CAMHS Commissioners: We will ask Commissioners who understand the current CAMHS referral processes locally or nationally, and who are involved in the funding process.
- Mental Health Leads: We will invite people with a strategic overview of the CAMHS referral process locally or nationally to share their experiences of the referral process.
- Any individuals identified through earlier WPs as key to the CAMHS referral process.
- Able to provide informed consent.
- Be proficient in English.

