6.2.2 Sampling technique

In WP1 and WP2, we shall use purposive sampling to recruit a diverse group of CAMHS stakeholders and Trust staff for focus groups.

In WP3, we shall use purposive sampling to include a diversity of referrers. We shall aim for diversity in terms of: type of referrer (GP, school, self-referrer, social care); CAMHS configuration (provision of service; location of CAMHS urban/rural) and by key individual characteristics of the referrer (age, ethnicity, spoken language etc). We shall aim to make the sample of referrers representative of the proportions of the different referrers that refer into CAMHS. That would mean more GPs than other referrers. The diversity of CAMHS configuration will be drawn from the data from EN-CAMHS 1 and with respect to relevant recent changes to the CAMHS landscape identified in WP1.

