8.2 Outputs

Key indicators of success will be defined by the following criteria:

- Digital referral platform successfully tested across minimum 5 CAMHS.
- Stakeholders successfully recruited to roundtable events and prioritisation of features consultation.
- CAMHS referral technical standards defined.
- Co-design of digital tool completed with outputs produced and published.
- Quantitative referral data collected and analysed from CAMHS sites. A reduction in the proportion of unsuccessful referrals is achieved when made through the ENCAMS platform compared to the usual referral processes.
- Following AMUsEd framework, engagement and usage metrics with the digital platform demonstrate that the platform is usable and acceptable to referrers.
- Qualitative intervention data successfully collected and analysed. Qualitative interviews demonstrate usability and acceptability of the platform to referrers and key stakeholders, including GPs, school staff, health and educational professionals and CYP and families/carers themselves. Qualitative interviews demonstrate a preference for the platform by referrers and key stakeholders, including GPs, school staff, health and educational professionals and CYP and families/carers themselves.
- Evaluation successfully completed.
- Sustainability plan developed that secures future plan for the CAMHS digital tool supported for use within the NHS.

Specific outputs for WP1

- Report detailing the changing CAMHS landscape (from roundtables) and how the digital tool aligns with newly configured CAMH services.
- Clear set of priorities and requirements for the revised CAMHS referral process, ranked by Must Have, Should Have, Could Have and Won't Have (MoSCoW) to enable the technical build in Work Package 2.
- A set of technical referral standards for the digital tool for development in WP2.

Finally, we aim to produce 4 peer-reviewed academic publications during the project.

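### Tool usage over time is read as acceptability, but it also reflects how many referrals each person has to make, so by itself it shows neither acceptance nor rejection

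*Protocol*

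**What the plan says.** Section 4.2 (WP3 quantitative analysis) states the inference directly: "we will summarise usage over time to evaluate whether it is an acceptable referral" method. It adds that "we will explore whether this differs between type of referrer". Section 8.2 lists among the success indicators that "engagement and usage metrics with the digital platform demonstrate that the platform is usable and acceptable to referrers". Acceptability and preference shown in interviews form a separate indicator there. Neither section relates usage to the number of referrals a participant had to make, or says what pattern would count as acceptable.

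The sample is mixed by design. Section 6.2.2 seeks diversity in "type of referrer (GP, school, self-referrer, social care"), and section 6.1.1 sets no minimum referral frequency for key referrers: "We would ask that these individuals have had experience referring CYP to CAMHS, regardless of how many times".

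Section 4.1 plans referral data from each referrer and from the receiving site: "We shall collect number of referrals made via the digital tools and numbers made by traditional referral mechanisms". It also plans counts of referrals completed to an endpoint, either CAMHS or alternative help. In section 4.2 the traditional-route data have one stated use: "We shall analyse the rate of successful referrals made using the tools against those made using traditional referral processes".

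**The concern.** Usage is the product of two things: how many referrals a person needs to make, and how often that person chooses the tool when one is needed. Only the second bears on acceptability. If the first changes over the evaluation, or differs between referrer types, the usage curve moves with it.

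The error can run in either direction. Fewer referrals to make could look like rejection of a tool that people still prefer. Growing demand could look like rising acceptance of a tool that people are leaving. Section 1 describes referral numbers as rising, while section 3.2 hopes to flatten that rise, so the protocol itself expects volume to move.

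At stake are the quantitative reading of acceptability, the comparison between referrer types, and the usage indicator in section 8.2.

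**Working it through.** The protocol states no figure on this point, so there is nothing to reproduce. The check is a deterministic illustration. Of its inputs, only the 60 referrers (section 6.2.1) come from the document; the rest are assumptions.

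**Formula.** Tool usage U = N × s, where N is referrals needed and s is the share made by the tool. Then s = tool / (tool + traditional).

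**Assumed inputs.**
- Twelve months from September, with s = 0.70 throughout.
- Mix of GP/school/family/social care: 30/15/10/5, 24/16/15/5 or 20/15/20/5.
- 0.25, 0.5 or 1.0 referrals a month for each professional.
- Each family refers once, within the first three months.
- School referrals in the last two months at 0%, 50% or 100% of the usual level.

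**One case in full.** Mix 24/16/15/5, 0.5 a month, schools at 50% in the last two months:

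| Type | Quarter 1 tool referrals | Quarter 4 tool referrals | Change |
|---|---|---|---|
| GP | 24 × 0.5 × 3 × 0.70 = 25.2 | 25.2 | 0% |
| School | 16 × 0.5 × 3 × 0.70 = 16.8 | 16 × 0.5 × (1 + 0.5 + 0.5) × 0.70 = 11.2 | −33% |
| Family | 15 × 0.70 = 10.5 | 0 | −100% |
| Social care | 5 × 0.5 × 3 × 0.70 = 5.25 | 5.25 | 0% |
| All | 57.75 | 41.65 | −28% |

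The share is 0.70 in every cell that has any referrals. The breakdown by type would show GPs steady and schools and families falling away, although no one's preference changed.

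**Range over all 27 combinations.**
- Smallest fall (30/15/10/5, 1.0 a month, no school drop): quarter 1 is (50 × 3 + 10) × 0.70 = 112 and quarter 4 is 150 × 0.70 = 105, a change of −6%.
- Largest fall (20/15/20/5, 0.25 a month, schools at zero in the last two months): quarter 1 is (40 × 0.25 × 3 + 20) × 0.70 = 35. Quarter 4 is (25 × 0.25 × 3 + 15 × 0.25 × 1) × 0.70 = 15.75, a change of −55%.

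**Opposite direction.** If s falls from 0.70 to 0.60, usage is unchanged when need grows by 0.70 / 0.60 = 1.17. Growth in need above about 17% would turn that loss of preference into a rising usage curve.

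Because s is held fixed, the constant share is true by construction. The illustration shows that usage cannot separate the two components; it does not predict what this study will see.

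**The case against.** **Usage is not the only evidence.** A reader might infer that the plan rests acceptability on usage alone. It does not. Section 3 combines quantitative and qualitative data, section 4.1 gives acceptability to interviews with 25 referrers, and section 8.2 has its own interview indicator. That stands. But the interviews cover 25 of 60, leaving 60 − 25 = 35 without one. Section 4.2 describes the interviewees as referrers who have used the tool, and the usage indicator is listed separately.

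**Research question 5.** A reader might infer that its answer would be wrong. It asks how referrers use and engage with the tool, and usage over time describes that whatever drives it. The concern is with acceptability, which belongs to research question 4.

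**Detail may sit in an analysis plan.** The metric, unit and denominator could properly be set there, and silence on a denominator is not a refusal of one. What the protocol does fix is the step from usage over time to acceptability, and it gives the traditional counts no part in that step.

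**Specific patterns are not documented.** It is tempting to say that family use drops to zero after one referral, or that a school summer break falls soon after launch. The protocol gives no referral frequencies, term-time effect or go-live date, only a WP3 window of months 12-24. The functions listed in section 2, such as progress updates and reusable referrals, mean that families may return to the tool after submitting.

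**Existing safeguards.** The breakdown by type would expose differing patterns but cannot separate fewer referrals from lower preference. The effective-engagement analysis addresses completion, not choice of route.

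**Stakes.** This is a feasibility study without hypothesis tests, and the comparison by type is exploratory. That limits the harm. Still, section 3 names evaluation of usage and acceptability as the study's purpose.

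**Conclusion.** The concern holds in a limited form. Section 4.2 reads acceptability from usage over time, and section 8.2 treats usage metrics as an indicator of it. Usage also carries referral opportunity, which can differ between the referrer types sampled. A trend or a difference between types is therefore not, by itself, evidence of acceptance or rejection.

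The size is unknown. The 6% to 55% range rests on assumed mixes, referral rates, school pattern and one-off family referrals, all at a fixed 70% share. The conclusion itself needs only that opportunity varies over time or between types. The protocol makes this plausible through its mixed sample and the absence of a minimum referral frequency, but does not quantify it.

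**What to change.** - In section 4.2, keep usage over time as the description for research question 5.
- For the quantitative reading of acceptability, report the share of each participant's CAMHS referrals made by the tool: tool divided by tool plus traditional. Present it by time since access and within referrer type.
- For participants with only one referral, use completion to an endpoint.
- Align the section 8.2 indicator with these measures and interpret it together with the interviews.

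The cost is wording in two sections. The counts by route and the endpoint data are already planned in section 4.1.

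Four limits should be stated with the measure:
- Shares are unstable for referrers with few referrals.
- They depend on which traditional counts each provider can capture, which section 4.1 leaves to the provider workshops.
- They should be confined to CAMHS referrals, because the tool's endpoints include alternative help that may have no recorded traditional counterpart.
- They may be raised because participants are recruited to use the tool.

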1 BACKGROUND

Children and young people's mental health is a national priority for the Department of Health and Social Care [1] and all major national funders. This research addresses critical problems in the referral processes to Child and Adolescent Mental Health Services (CAMHS) that we identified during our qualitative research program during our NIHR HS&DR-funded EN-CAMHS 1 project.

1. **CAMHS cannot cope with the growing numbers of referrals.** Nearly 500,000 children and young people (CYP) were referred to CAMHS in 2021/2022 [2], and this number has risen steadily since 1999 [3,4]. CAMHS providers are overwhelmed by the number of referrals [5,6].
2. **Rising demand is coupled with high levels of rejection.** Almost a quarter of the referrals made into CAMHS are unsuccessful because they are deemed inappropriate or do not reach the threshold for treatment [2]. This results in **longer delays for children who need the specialist care**, which is exacerbating mental health difficulties [7].
3. The **experience of the referral process is poor** [8,9]. The high rate of inappropriate referrals causes **unnecessary distress to children, their families and to referrers**, who can wait many weeks if not months for a decision [10]. The family upset is compounded by **a lack of communication throughout the long process** [11]. When a referral is rejected, it typically goes to the 'back of the queue', resulting in further delays for children and families.
4. **The quality of CAMHS referrals is poor** and is often the first and only, service referred to by families (who see this as the gold standard) and **referrers struggling to know what else is available** in primary care [7,10]. This leads to an increased number of referrals, which are often not completed to the standard needed by CAMHS.
5. Clear **information** about what CAMHS can and cannot provide is **not readily available and suitable alternative sources of mental health support are often not explained** to children and their families at the point of referral rejection [12,13].
6. Non-CAMHS support is **poorly understood** [14] and not widely valued as a helpful source of support. People who could be helped better by non-CAMHS support are **not signposted elsewhere early enough** in the process, except in a minority of places.

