3 RESEARCH QUESTION/AIM(S)

Our overarching aim is to improve the CAMHS referral process for CYP, their families and carers, as well as for health, education and CAMHS professionals so that CYP receive the help they need as quickly as possible.

Research questions:

1. Using the findings from EN-CAMHS 1 and stakeholder consultation, can we develop a set of national standards for digital CAMHS referral processes?
2. Can we translate the prioritised features from EN-CAMHS 1 of a digitally-led, intelligent CAMHS referral process into a usable, acceptable and widely accessible platform that is nationally standardised, locally adaptable and sustainable?
3. Can we address concerns about digital exclusion and other identified health inequalities through the newly developed CAMHS referral mechanisms?
4. How do referrers, including GPs, school staff and children/young people/families perceive the usability and acceptability of the digital tool?
5. How do referrers use and engage with the tool?
6. How do rates of successful referrals with the tool compare to traditional modes of referral?

There are no primary nor secondary outcome measures for this study as this is a feasibility study to evaluate usage and acceptability of the co-created tool using data collected from referrers. These data will be a combination of quantitative data on usage and engagement and qualitative data from semi-structured interviews with 25 referrers.

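### Section 4.2 defines a successful referral without acceptance by CAMHS, then uses the term for the tool-versus-traditional comparison, against the Background's meaning

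*Protocol*

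**What the plan says.** Section 4.2 (WP3 quantitative analysis) introduces the term while describing effective engagement with the tool, meaning referrers' ability to complete a referral. It then defines it: "A successful referral can mean either a referral to CAMHS or to an alternative source of support for the CYP". The following sentence carries the term into the comparison: "We shall analyse the rate of successful referrals made using the tools against those made using traditional referral processes". That is research question 6 in section 3: "How do rates of successful referrals with the tool compare to traditional modes of referral".

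Three other places bear on the meaning:

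- Section 1 (Background): "Almost a quarter of the referrals made into CAMHS are unsuccessful because they are deemed inappropriate or do not reach the threshold for treatment".
- Section 8.2 (Outputs), as a key indicator of success: "A reduction in the proportion of unsuccessful referrals is achieved when made through the ENCAMS platform compared to the usual referral processes". Unsuccessful is not defined there.
- Section 4.1 (Data Collection, WP3) plans usage data from the tool, "including numbers of referrals completed to an endpoint (either referral sent to CAMHS or to alternative help"), and separately: "We shall collect data on accepted/rejected referrals made by participant referrers to CAMHS using a) the tool and b) traditional modes of referral".

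No sentence links the accepted/rejected data to the success rate in section 4.2.

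**The concern.** The section 4.2 definition almost repeats the tool's completion endpoint in section 4.1. It describes a referral that reached a destination, whatever CAMHS then decided. As a measure of engagement with the tool that is reasonable. As the outcome of the comparison it is not, because a referral that CAMHS receives and rejects is a success under section 4.2 and unsuccessful under the Background. Section 8.2 can be read either way.

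Two things are at stake. Read literally, the comparison cannot register a change in rejected referrals, which is the problem the study was set up to address. If success is instead read as accepted or diverted, section 4.1 specifies the alternative-help endpoint only within the tool's usage data. For traditional modes it names numbers of referrals and their acceptance or rejection by CAMHS. The tool could then gain credit for an outcome not recorded for its comparator.

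Section 3.2 also lists a lower proportion of inappropriate referrals and a higher proportion of successful ones as separate anticipated effects. One rate without a settled definition cannot report on both.

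**Working it through.** The protocol gives no figure to reproduce: section 6.3.1 states that no power calculation was made and that hypothesis testing is not the aim. The check compares what each reading of success would return.

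**Inputs**

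- Rejection under traditional referral: 24%, taken from the Background's almost a quarter, so 76% are accepted.
- *d*, the share of tool referrals diverted to other support: not in the protocol, assumed.
- *q*, the share of diverted referrals that CAMHS would have rejected: not in the protocol, assumed. If diversion is unrelated to acceptability, *q* = 0.24.

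**Step 1: literal definition.** Every submitted referral goes to CAMHS or elsewhere, so the rate is 100% versus 100%, whether the tool's rejection rate is 24% or 12%. With started referrals as denominator and 10% abandoned (assumed), the tool scores 90% at either rejection rate. The measure does not respond to rejection.

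**Step 2: four readings side by side.** Take 24% rejection among referrals sent to CAMHS in both modes, and *d* = 0.20 unrelated to acceptability.

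| Reading of success | Tool | Traditional |
|---|---|---|
| Sent to CAMHS or diverted (literal) | 100% | 100% |
| Accepted / sent to CAMHS | 0.608/0.80 = 76% | 76% |
| Accepted or diverted / all completed | 0.608 + 0.20 = 80.8% | 76% |
| Accepted / all completed | 0.80 × 0.76 = 60.8% | 76% |

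Over rejection of 20% to 25% and diversion of 0% to 20%, tool minus traditional is always 0 for the first two readings, 0 to +5 points for the third and 0 to −16 points for the fourth. The definition alone decides the sign.

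**Step 3: gain when diversion counts for the tool only.** Accepted = 0.76 − *d*(1 − *q*). Adding the diverted share gives 0.76 + *dq*, so the gain is *dq*.

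- *q* = 0.24 and *d* = 0.10, 0.20, 0.30: rates 78.4%, 80.8%, 83.2%; gains 2.4, 4.8, 7.2 points.
- *d* = 0.12 and *q* = 0, 0.24, 1: gains 0, 2.9, 12 points. Where diverted referrals would have been rejected, part of the gain is real.

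**Step 4: what separates these cases.** At *d* = 0.12, acceptance among submitted referrals is (0.76 − 0.12(1 − *q*))/0.88.

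| *q* | Accepted / rejected / diverted, % of completed | Accepted among submitted |
|---|---|---|
| 0 | 64 / 24 / 12 | 0.64/0.88 = 72.7% |
| 0.24 | 66.9 / 21.1 / 12 | 0.6688/0.88 = 76.0% |
| 1 | 76 / 12 / 12 | 0.76/0.88 = 86.4% |
| Traditional | 76 / 24 / 0 | 76% |

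Acceptance among submitted referrals therefore also depends on who is diverted. The three-way split shows which case applies; no single rate does.

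**The case against.** The strongest reply is that the literal reading is not the intended one. The definition says what success can mean, names two destinations and does not say that acceptance is irrelevant. Section 4.1 plans accepted/rejected data for both modes, separately from completion, which mirrors research question 6. On this view one linking sentence is missing, and the Background merely reports a national figure. That is fair about intent, and it makes the repair cheap. It does not remove the clash: no passage adds acceptance to the definition, and the comparison follows it directly. Nor is this detail left to an SAP, since the protocol itself states the definition and applies it.

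Counting diversion as success also looks deliberate. Section 2 presents signposting to other support as a way to improve referral success, and section 4.1 says "We shall collect referral data from each referrer and from the CAMHS site referred into", which might capture diversion under traditional referral. Both points stand in part. Diversion should stay visible, but equal recording is not stated. The provider workshops are to establish which data can be captured and how they are recorded, not what counts as success.

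Finally, the evaluation is non-randomised, has no primary or secondary outcomes, and the sizes above rest on assumed shares. All true, and this limits the consequence. Preferring acceptance among submitted referrals is not neutral either, as step 4 shows, so that measure needs its own caveat.

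**Conclusion.** The concern holds and should be fixed. The protocol's only definition of a successful referral measures completion, is applied to a comparison meant to inform on rejection, and conflicts with the Background, leaving the section 8.2 indicator open to more than one reading.

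Read literally, the comparison among submitted referrals is 100% versus 100% whatever happens to rejection. Read as accepted or diverted, with diversion recorded for the tool only, the gain is 2.4 to 7.2 points for 10% to 30% diverted when diversion is unrelated to acceptability, and 0 to 12 points at 12% diverted depending on who is diverted. Only the starting rejection rate is anchored in the protocol; the diversion, abandonment and halved-rejection figures are assumptions, so these sizes are illustrations and not estimates for this study. No error rate or sample size is involved.

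**What to change.** 1. For research question 6 and the section 8.2 indicator, report CAMHS accepted versus rejected among referrals submitted to CAMHS, defined identically in both modes from the data planned in section 4.1. Show undecided referrals separately.
2. Always show beside it the number and share of tool referrals diverted to other support, for example as accepted/rejected/diverted shares of all completed referrals.
3. State that acceptance among submitted referrals depends on who is diverted and is not by itself a neutral measure of the tool's effect.
4. Count diversion as success in the comparison only if it is recorded in the same way for traditional referrals.
5. Keep the tool-only completion measure under effective engagement, but stop calling it a successful referral.

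The cost is protocol wording: accepted/rejected data are already planned for both modes, and diversion counts are already in the tool's usage data. Recording diversion for traditional referrals would be extra work, needed only if it is to count as success in the comparison. The downside is that the tool's headline rate may look less favourable, and appropriate diversion, an intended benefit, appears beside the comparison and not inside it.
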